5.3 Strategies for Recruitment and Retention

Five Chinese American community-based organizations have already volunteered to participate in this study. The 3 outreach centers for this study will be selected from among the affiliated outreach centers of these organizations.

Adults served by the outreach centers will be recruited by NYU research staff working with 3 Chinese American community sites in New York, NY.

EHR patient participants (of whom certain individuals are also interview patient participants) will receive a voucher worth \$205 for oral health care at NYU Dentistry to

cover her/his comprehensive oral examination, treatment plan, and prophylaxis at no charge and with no co-payment required as compensation for participation.

Non-patient participants--research staff, NYU administrators, providers (dentists and CHWs), outreach site directors, and CAB members--will receive no monetary compensation for their participation in the study, over and above their salaries/stipends.

5.4 Subject Withdrawal

5.4.1 Reasons for Withdrawal

Any of the various participants (i.e., CAB members, outreach site directors, EHR patient subjects, interview patient subjects, research staff, NYU administrators, dentists, and CHWs) may withdraw from the study at any time. Patients will have the right to refuse to participate without any compromise of their health or dental services. Also, if a participant is uncomfortable during an interview or survey administration, s/he may stop at any time without penalty.

5.4.2 Handling of Subject Withdrawals or Subject Discontinuation of Study Intervention

If an EHR patient participant withdraws consent, no further data from that patient will be entered into the EHR for that participant. Depending on the nature of the request to withdraw, it may be necessary to remove existing data for that patient from the EHR.

5.5 Premature Termination or Suspension of Study

This study has no explicit stopping rules. The study may be suspended or prematurely terminated if there is sufficient reasonable cause. Written notification, documenting the reason for study suspension or termination, will be provided by the suspending or terminating party to the MPIs and/or the NIDCR, as applicable. If the study is prematurely terminated or suspended, the MPIs will promptly inform the Institutional Review Boards (IRBs) and provide the reason(s) for the termination or suspension.

Circumstances that may warrant termination include, but are not limited to:

- Determination of an unexpected, significant, or unacceptable risk to participants.
 - Insufficient adherence to protocol requirements.
 - Data that are not sufficiently complete and/or evaluable.
-

6 STUDY INTERVENTION

6.1 Administration of Intervention

Initially a CAB will be established to guide all aspects of the study.

Partnered intervention: Our partnering package of interventions builds upon the evidence-based practices of the NYU Dentistry Local Community Outreach Programs and the results of our pilot study in the Sikh American community, and aligns with the implementation strategies from the Expert Recommendations for Implementing Change (EPIC) project. We will work closely with the directors of 3 Chinese American outreach sites to create written agreements of collaboration that outline the roles and responsibilities of the investigative team and the sites. An integral part of effectively implementing oral health activities with low-income, racial and ethnic minority, and immigrant populations, including Chinese Americans, is to develop program materials that are specific to the local community. Training lay individuals of the same cultural and linguistic background as participants, e.g., CHWs through train-the-trainer techniques, has been found to be an acceptable approach for delivering culturally-appropriate, community-based oral health interventions as well as for recruiting participants into interventions through community and social networks. CHWs have been found to be effective in providing dental education and counseling, leading interactive demonstrations of brushing with fluoride toothpaste and flossing, and improving access to dental care through dental coverage enrollment and linkage to local dentists.

Development of culturally-tailored and language-specific materials: The CAB will be responsible for reviewing existing program materials as an integral part of adapting them for the local Chinese American population. This will entail a multi-step process. Existing English and simplified Mandarin Chinese language materials will be presented to the CAB. [name] will then lead a guided discussion structured around the 4 P's of social marketing. For product, CAB members will be asked if the materials encourage prevention of oral conditions through regular dental visits and brushing with fluoride toothpaste. For price, CAB members will be asked how much it will cost a person to take on the desired behaviors in terms of time and effort, not merely dollars and cents. For place, CAB members will be asked to help compile a list of local dental providers in addition to NYU Dentistry who provide culturally-tailored and language-specific oral health care to Chinese American families. For promotion, CAB members will be asked to identify other Chinese American community change agents to promote the program through word of mouth, social media, and neighborhood venues. CAB input will also be sought on incorporating appropriate imagery and cultural beliefs regarding oral health in the Chinese American community. This guidance will then be used to adapt both print and online materials. Finally, the adapted materials will be presented back to the CAB to ensure their input was accurately captured.

6.2 Procedures for Training Interventionists and Monitoring Intervention Fidelity

Both CHWs in this study were formerly trained as CHWs, have a history of engaging in health promotion with the Chinese American community, and are bilingual in English and Mandarin Chinese (the primary dialect of participating community outreach sites). Specifically, the project CHWs were previously trained in a core competency program that employed diverse training methods, guided by adult learning principles and popular education philosophy. We will further train the project CHWs in the oral health promotion demonstration protocol and on oral health services and programs available at local clinics and hospitals. The investigative team and CAB members will also collect, assess, and deliver to the CHWs updated information regarding health and dental insurance and access to oral health programs available for low-income and immigrant communities. NYU Dentistry investigators and staff will train the CHWs using models on evidence-based oral health practices, stressing the importance of drinking fluoridated water and brushing teeth for 2 minutes twice a day with a soft-bristled toothbrush and fluoride toothpaste. This train-the-trainer model will promote peer support and allow the project to be replicated and sustained across settings. Interactive educational techniques will be integrated into the demonstrations.

6.3 Assessment of Subject Compliance with Study Intervention

Not applicable. There is no assessment of subject compliance.

7 STUDY SCHEDULE

The study will extend for approximately 1 year. An approximate timeline for implementation of the various aspects of this study is as follows:

Table 2. Timeline of study activities

Study activities	Months 1-6	Months 7-12
Recruitment of CAB and outreach sites		
Review, update, and finalize CHW training materials / IRB		
Train CHW, evaluate fidelity, retrain as necessary		
Implement partnered intervention		
**Exit and 1 month follow-up interviews of enrolled patients who participated in the partnered intervention		
**Semi-structured interviews of non-patient participants regarding partnered intervention (including materials review prior to implementation)		
Workflow analysis for remote EHR entry		
Pilot testing and live-usability for remote EHR		
**Semi-structured interviews of non-patient participants in EHR implementation.		
**Semi-structured interviews of non-patient participants to inform model		
**Group model-building workshop		
Development of simulation modeling platform		

***Data collection activity.*

7.1 Pre-intervention Activities

- Create written agreements of collaboration that outline the roles and responsibilities of the investigative team and the outreach sites
- Develop culturally-tailored and language-specific program materials
- Train CHWs in the intervention protocol
- Conduct a workflow analysis of remote EHR data entry at Chinese American outreach centers

7.2 Outreach Center Activities

- Health Insurance Portability and Accountability Act (HIPAA) certified research staff members or volunteers will explain the consent form, confidentiality agreement, and liability release to each potential patient participant and obtain her/his signature
- Remote EHR Data Collection and Dental Screening:

-
- Authorized NYU Dentistry personnel will directly enter the demographic information of patient participants into the customized EHR using the study-specific SCREENING option
 - EHR patient participants will complete a short paper intake form that will be scanned directly into a designated SCREENING folder in the EHR regarding medical conditions that could affect, or be affected by, their oral health (Yes / No checklist) and a brief questionnaire on self-reported receipt of a dental visit in the past year and dental hygiene behaviors (Oral Health Survey). These questions will be based on the World Health Organization (WHO) Oral Health Questionnaire for Adults: (1) How often do you clean your teeth? (Never, Once a month, 2-3 times a month, Once a week, 2-6 times a week, Once a day, Twice or more a day); (2) Do you use any of the following to clean your teeth? (Toothbrush, Wooden toothpicks, Plastic toothpicks, Thread (dental floss), Charcoal, Chewstick / miswak, Other (Please specify)); (3) For those who nominate Toothbrush: What type of toothbrush do you use? (Hard-bristled, Medium-bristled, Soft-bristled) (4) Do you use toothpaste to clean your teeth? (5) For those who nominate Toothpaste, Do you use a toothpaste that contains fluoride? Correct responses to all 5 questions will indicate that EHR patient participants are following the guidance of the American Dental Association (ADA) on brushing with fluoride toothpaste. These measures will be collected in person via self-report to ascertain baseline status at the beginning of each screening event and scanned directly into the NYU Dentistry remote EHR customized for community outreach events.
 - An NYU Dentistry faculty dentist will conduct a head and neck / oral examination on each EHR patient participant and directly enter the results into the customized EHR
- The dentist will review the examination results with the EHR patient participant using a customized walkout statement with screening results and follow-up notes and answer any questions regarding oral health concerns
 - CHW Initial Intervention: Trained CHWs will deliver a culturally-tailored and language-specific oral health promotion program focusing on demonstrations with role-playing of proper brushing with fluoride toothpaste and flossing techniques. They will also provide culturally customized literature to the patients.
 - Acceptability Data Collection: Research staff will conduct a brief exit interview with each interview patient participant regarding acceptability of
-

the intervention and self-efficacy around oral health behaviors, requesting permission to contact her/his regular dental provider regarding receipt of a follow-up dental visit and providing a voucher worth \$205.00 for oral health care at NYU Dentistry to cover her/his comprehensive oral examination, treatment plan, and prophylaxis at no charge and with no co-payment required. The questions for this survey will be based on our previous oral health promotion program in the Sikh American community to assess acceptability. Prior to finalizing the survey for distribution to the interview patient participants, CAB members and research staff will adapt the questions as deemed appropriate for the Chinese American community and to be consistent with the ADA guidance on brushing with fluoride toothpaste.

- Feasibility Data Collection: We will also develop a checklist of 10 key components based on process (e.g., patient engagement) and the curriculum (e.g., topics covered) and ask if each one was covered. Endorsement of 8 of the 10 checklist items (80%) by the non-patient participants will be considered as the bar for success for feasibility. Finally, we will allow for open-ended collection of feedback on the feasibility of each of the partnered program components.

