The partnered intervention consists of the following 4 evidence-based strategies: (1) written agreements of collaboration for dental screening at the site level; (2) culturally-tailored and language-specific adaptation of materials at the community and site levels; (3) demonstrations with role-playing of proper brushing with fluoride toothpaste and flossing techniques at the site and provider levels; and (4) community health worker (CHW) follow-up with patients about oral health care receipt and dental hygiene behaviors at the family and patient levels.

[figure not shown]
Patient Participants

Patient participants refer to study participants who are also patients screened at the urban outreach centers. Patient participants are first enrolled as EHR patient participants as part of the feasibility and acceptability study of this form of patient tracking. A subset of the EHR patient participants also complete exit interviews after the intervention at urban outreach centers and are referred to as interview patient participants.

Non-Patient
Participants

Non-patient participants refer to all other study participants who are not patients screened at the urban outreach centers, including community advisory board (CAB) members, research staff, New York University (NYU) administrators, providers (dentists and CHWs), and outreach site directors.

PROTOCOL SUMMARY

Title: Implementing a Participatory, Multi-level Intervention to Improve Asian American Health

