- (a) the services performed do not merit professional recognition or publication privileges;
- (b) the services performed are typically performed by those institutions for non-research purposes; and
- (c) the institution's employees or agents do not administer any study intervention being tested or evaluated under the protocol.

The following organizations provided letters of support, which will form the basis for selecting 3 community outreach centers and 8 CAB members for this F & A study:

- Asian Americans for Equality (AAFE)
- Chinatown YMCA, a branch of the YMCA of Greater New York
- Chinese-American Planning Council (CPC)
- Coalition for Asian American Children and Families (CACF)
- Hamilton-Madison House (HMH)

Moreover, 2 NYU centers provided letters of support for this feasibility and acceptability study.

- Integrating Special Populations Unit, New York University Health and Hospitals Corporation (NYU-H+H) Clinical and Translational Science Institute (CTSI)
- NYU-H+H CTSI

Description of Intervention:

The aspects of the partnering package of evidence-based intervention strategies are: (1) written agreements of collaboration for dental screening, health promotion, and incentives; (2) culturally-tailored and language-specific adaptation of materials; (3) demonstrations with role-playing of proper brushing with fluoride toothpaste and flossing techniques; and (4) CHW follow-up with patients of oral health care receipt and dental hygiene behaviors.

Additionally, bilingual (English and Mandarin Chinese) CHWs will

receive additional training in oral health promotion demonstration, oral health services and programs available at local clinics and hospitals, information about dental and health insurance, and evidence-based oral health behaviors.

Study Duration: 1 year

[figure not shown]
Subject Participation Duration: Participation duration refers specifically to the period of time when data are collected from individual participants. It does not capture periods of time when individual participants are remotely entering EHR data or administering aspects of the intervention or protocol. That information is captured elsewhere in this protocol.

- 1 year for the community outreach centers
- 1 or more days for each research staff member, NYU administrator, provider (dentist or CHW), CAB member, or outreach site director to respond to questions about the partnered intervention and/or the remote EHR implementation

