12.4 Final Analysis Plan

Acceptability of the partnered intervention will be assessed through exit interviews of the interview patient participants.

As we did with the Sikh American project, we will utilize a pre-post retrospective evaluation design. In this format, all questions will be asked in a single exit interview, but where applicable, will use the phrasing, "Prior to the beginning of the program..." followed by, "At the present time..." Table 3 lists the questions/domains we will use, and expected % changes we hypothesize we will observe in the current study. The percent change from pre-post will be compared using t-tests for proportions. Given that many of the answer choices are non-binary, we will also compare the shift of responses from pre-post across the categories of response using chi-squared tests. Note that this is not an exhaustive list of questions that will be asked; we are simply highlighting those questions that we will use to quantify acceptability. The full planned questionnaire is attached.

Health care utilization and oral health promotion measures: Our ultimate health care utilization measure of interest is receipt of a dental visit within the last 12 months. This will be measured using the Medical Expenditure Panel Survey (MEPS) definition, where dental visit refers to care by or visits to any type of dental provider. This will allow for

direct comparison with Healthy People 2020 Leading Health Indicator OH-7 to increase the proportion of children, adolescents, and adults who used the oral health care system in the past year.

Our central oral health promotion measure is self-reported brushing of teeth for 2 minutes twice a day with a soft-bristled toothbrush and fluoride toothpaste at the interview patient participant's 1 month follow-up visit. For the primary health care utilization measure of receipt of a dental visit within the last 12 months, we will also access the NYU Dentistry EHR database and follow-up with oral health care providers identified by participants in HIPAA approved procedures to ascertain receipt of a dental visit in the last 12 months.

Table 3 provides the measures and definitions of the oral health promotion, self-efficacy, and acceptability measures used in our prior research with the Sikh American community that will be adapted for the present F & A study with the Chinese American community.

Table 3. Measures and definitions of oral health promotion, self-efficacy, and acceptability measures

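### A $205 free-care voucher pays for a visit that counts toward the dental-visit measure and is handed over inside the satisfaction interview; the plan neither separates voucher visits nor settles whether the voucher belongs to the package

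*Combined protocol and SAP*

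**What the plan says.** Section 5.3 (Strategies for Recruitment and Retention): "EHR patient participants (of whom certain individuals are also interview patient participants) will receive a voucher worth" $205 at NYU Dentistry, to "cover her/his comprehensive oral examination, treatment plan, and prophylaxis at no charge and with no co-payment required as compensation for participation". This covers all 150 EHR patient participants, including the 90 or so who are interviewed. No condition on interview answers is stated.

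Section 7.2 (Outreach Center Activities) describes the hand-over under the exit interview. Research staff ask about acceptability and self-efficacy, and the same sentence has them "requesting permission to contact her/his regular dental provider regarding receipt of a follow-up dental visit and providing a voucher worth" $205. No other hand-over point is described.

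Section 12.4 (Final Analysis Plan): "Our ultimate health care utilization measure of interest is receipt of a dental visit within the last 12 months". The definition takes in care from any type of dental provider, and the NYU Dentistry EHR is one of the sources used to confirm visits. Section 7.3 has the CHW ask at about 1 month whether a visit has been received or scheduled. Neither section mentions voucher use.

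The package is defined twice. Under Special Terms, strategy 1 is "1) written agreements of collaboration for dental screening at the site level". In the Protocol Summary (Description of Intervention) it is "1) written agreements of collaboration for dental screening, health promotion, and incentives". Incentives are not defined there, and section 5.3 classes the voucher as compensation.

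The primary outcome (section 3.2.1) is patient satisfaction with the intervention components, taken from the exit interviews. Section 12.4 sets the acceptability bar at 80% or more of interview participants agreeing or strongly agreeing with all four items.

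**The concern.** The voucher bears on two results.

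First, it pays for an event that the utilization measure counts. Someone who redeems it has had a dental visit, at the institution whose records are used to confirm visits. The study exists to inform a larger randomized trial. If the designers of that trial take over an uptake figure, they need to know how much of it came through free care, and whether free care is part of what they would be testing. As written, the plan answers neither question.

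Second, a benefit worth $205 is provided in the interview that produces the primary ratings, by the staff who collect them. Participants may rate the program more kindly for that reason, and the result is judged against a fixed bar.

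There is also a practical gap. Section 5.3 promises the voucher to all 150, but the only hand-over described belongs to an interview that about 60 of them do not have.

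**Working it through.** **1. Counts.** Section 5.1 plans 3 × 50 = 150 EHR patient participants and 3 × 30 = 90 interview participants. Its expectation that about 60% complete the interviews gives 0.60 × 150 = 90, so the plan's own figure reproduces. EHR-only participants: 150 − 90 = 60, or 60/150 = 40%.

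**2. Does redeeming the voucher count as the measured event?** Section 7.2 describes the voucher as worth $"205.00 for oral health care at NYU Dentistry to cover her/his comprehensive oral examination, treatment plan, and prophylaxis at no charge". Section 12.4 counts care by any dental provider and excludes no visit because of who paid. So a redeemed voucher is a counted visit. The section 7.3 question also takes in scheduled visits, so an appointment booked on the voucher would count there as well.

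**3. Is the voucher part of the package?** Three places, set side by side:
- Special Terms: four strategies, no incentive.
- Protocol Summary: the same four, with undefined incentives inside strategy 1.
- Section 5.3: the voucher is compensation for taking part.

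These cannot all be read the same way. If the voucher is compensation, it is a co-intervention. If it is part of the package, Special Terms and section 5.3 need to say so.

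**4. What can one arm show about visits?** The documents give no expected visit rate, so these figures are assumptions. Take observed uptake of 70%, let b be the share who would have had a visit anyway, v the points added by the voucher, and let effects add. The package's share is 70 − b − v points.

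| b | v = 0 | v = 10 | v = 20 | v = 30 |
|---|---|---|---|---|
| 40 | 30 | 20 | 10 | 0 |
| 20 | 50 | 40 | 30 | 20 |

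Every cell gives the same observed 70%. When everyone is offered the voucher, the data cannot choose among them.

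**5. How sensitive is the acceptability bar?** 80% of 90 is 0.80 × 90 = 72. The chance of passing is the exact binomial tail P(X ≥ 72) with n = 90 and success probability p:

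| p | P(X ≥ 72) |
|---|---|
| 0.70 | 2.2% |
| 0.75 | 16.5% |
| 0.80 | 56.3% |
| 0.85 | 92.6% |

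With a true rate of 70%, an upward shift of 5, 10 or 15 points moves the chance of passing from 2.2% to 16.5%, 56.3% or 92.6%. With a true rate of 75%, shifts of 5 and 10 points move it from 16.5% to 56.3% and 92.6%. The shifts are assumed; the documents give no size for a goodwill effect.

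**The case against.** **Satisfaction.** The four items in Table 3 ask about the CHW (two items), the information and the demonstrations. None asks about the voucher. Every EHR participant is to receive it, with no stated link to answers, and section 5.4.1 lets anyone stop an interview without penalty. Section 7.2 names the voucher last and does not say whether it comes before or after the ratings. Section 12.4 says the full questionnaire is attached; it was not in the text available here and may settle the order. All of this stands. A reader might infer that the voucher makes the satisfaction result unreadable. The documents do not support that: the ratings remain ratings of named components, possibly inflated by an unknown amount. Moving the hand-over also removes only part of any goodwill if participants already know the voucher is coming.

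**Visits.** No control group is described. The dental visit is not the primary outcome, is not listed in Table 1, and has no expected rate or success bar. Attribution to the package would be out of reach without the voucher too, and no section says uptake will be credited to the CHWs. A 12-month look-back asked about 1 month after the event also reaches mostly into the time before the program. These points limit the weight of the concern. They do not explain why a known source of visits, one the plan itself supplies, should go unrecorded.

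**Splitting by voucher use.** A reader might take the non-voucher rate as the package's effect. That would be wrong. Under section 7.3 the CHW may help book a visit at NYU Dentistry, so a redeemed visit can be partly the CHW's work, and some redeemed visits would have happened anyway.

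**EHR-only participants.** A reader might infer that the 60 or so without an exit interview get no voucher. Section 7.2 does not say that only interviewees receive it, and section 5.3 says all EHR participants do. This is an undescribed step.

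**Conclusion.** The concern holds in a limited form, and the plan should be changed.

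- Voucher-paid visits are pooled into the utilization measure, so reported uptake is uptake under the package plus free care. The documents give no basis for a size; the table of splits shows only that the share cannot be recovered from one arm.
- Whether the voucher belongs to the package is unsettled among Special Terms, the Protocol Summary and section 5.3.
- Providing the voucher within the rating interview may push the primary ratings up. The pass or fail result is sensitive to modest shifts: under an assumed true rate of 70%, 10 points would raise the chance of passing from 2.2% to 56.3%. That such a shift occurs is an assumption. The binomial figures also assume 90 completed interviews and independent responses.
- No hand-over is described for about 60 of the 150 participants (40%). This is a gap in procedure.

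**What to change.** 1. **Sections 7.3 and 12.4.** For each follow-up visit, received or scheduled, record whether the voucher was or will be used. Add one question to the 1-month CHW contact, and use NYU Dentistry records as well if they show redemption; the documents do not say that they do. Report visits overall and by voucher use. Describe uptake as package plus voucher, and do not present the non-voucher rate as the package's effect.
2. **Section 7.2.** Give the voucher to all 150 participants at one point outside the rating interview. Someone other than the interviewer should do this where existing staff allow; otherwise it should follow completion of the ratings. Tell participants that it does not depend on their answers. This also closes the gap for EHR-only participants.
3. **Special Terms, Protocol Summary and section 5.3.** Reconcile them on whether the voucher is part of the package or compensation.

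Cost: one more question, one more table row and wording changes, with no added participants or visits. The visit result may look less favourable once split. The split is descriptive and cannot isolate the voucher's causal effect.
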